8.1.7 Supervised Use of Acclimatization Dentifrice

Eligible subjects will be provided with the acclimatization dentifrice, toothbrush, diary and timer to use during the acclimatization period (2-4 weeks). Dentifrice usage instructions will be described to the subject and dosing of a full brush head with dentifrice will be demonstrated. Staff will supervise the subject carrying out first dosing/brushing with acclimatization dentifrice and recording first use in their diary. Completion of all procedures will be documented in the CRF.

Spontaneous reporting of adverse events and those elicited by asking subjects to respond to a non-leading question such as "How do you feel?" will be assessed. Any AEs/incidents reported on completion of the supervised brushing with the acclimatization dentifrice will be recorded in the CRF.

8.2 Study Period

8.2.1 Baseline: Day 0 (Visit 2)

Changes in health, concomitant medication or non-drug treatments/procedures will be documented in the CRF.

Spontaneous reporting of adverse events and those elicited by asking subjects to respond to a non-leading question such as "How do you feel?" will be assessed and any AEs recorded in the CRF.

The following procedures will then be completed.

- Complete visual checks of returned acclimatization dentifrice tubes and review completed diary. Record any suspected over or under use, and the number of any missed or additional brushings, in the CRF.
Do not return acclimatization dentifrice/toothbrush/diary to subject.
- Female subjects of child-bearing potential *only* complete a UPT. Record the result in the CRF.
- Subject completes a DHEQ (source document), for later transcription into the CRF.
- Clinical examiner completes an OST examination. Record findings in the CRF.
- Clinical examiner completes an OHT examination. Record findings in the CRF.
- Clinical examiner completes sensitivity assessments for each eligible tooth identified at Screening (eligible incisors, canines, pre-molars, with a tactile threshold of ≤ 20 g and a Schiff sensitivity score ≥ 2), first to a tactile stimulus

and then to an evaporative air stimulus. The examiner will allow at least 5 minutes between the completion of the tactile assessments and the start the evaporative air assessments for tooth recovery. Record clinical assessment scores in the CRF or using source documentation for later transfer to the CRF. The same examiner will be responsible for completing both clinical measures of DH (tactile and evaporative air sensitivity) for the duration of the study.

- Clinical examiner reviews inclusion and exclusion criteria and confirms subject eligibility in the CRF. Subjects with at least 2 sensitive teeth (tactile threshold \leq 20 g; Schiff sensitivity score \geq 2 at Screening and Baseline) will continue.
- Clinical examiner selects the two ‘test teeth’ for sensitivity assessment at subsequent study visits. Record in the CRF.
- Complete stratification and randomization.
- Dispense allocated study dentifrice, toothbrush and diary. Record in the CRF.
- Describe dentifrice usage instructions and diary completion to subject; supervise their first dosing and brushing with study dentifrice and recording of brushing in the diary. Record in the CRF.
- Spontaneous reporting of adverse events and those elicited by asking subjects to respond to a non-leading question such as “How do you feel?” will be assessed. Any AEs/incidents reported on completion of the supervised brushing with the assigned study dentifrice will be recorded in the CRF.
- Remind the subject of the Lifestyle Guidelines ([Section 5.5](#)) and any Concomitant Medication/Treatment(s) requirements ([Section 6.8](#)) of the protocol. Record in the CRF.

8.2.2 Day 3, Day 7 (+1 day), Day 14 (± 1 day) and Day 28 (± 2 days) (Visits 3-6)

Changes in health, concomitant medication or non-drug treatments/procedures will be documented in the CRF.

Spontaneous reporting of adverse events and those elicited by asking subjects to respond to a non-leading question such as “How do you feel?” will be assessed and any AEs recorded in the CRF.

The following procedures will then be completed at each visit.

- Complete visual checks of returned study dentifrice tubes and review completed diary. Record any suspected over or under use, and the number of any missed or additional brushings, in the CRF. Re-instruct the subject in the correct dosing, usage requirements and diary completion as needed.

Return dentifrice/toothbrush/diary to subject.

- Confirm subject adherence to the requirements of the protocol and continuance. Record in the CRF.
- ***Day 28 (Visit 6) only:*** Subject completes a DHEQ (source document), for later transcription into the CRF.
- Clinical examiner completes an OST examination. Record findings in the CRF.
- Clinical examiner completes sensitivity assessments for the two 'test teeth' selected at Baseline, first to a tactile stimulus and then to an evaporative air stimulus. The examiner will allow at least 5 minutes between the completion of the tactile assessments and the start the evaporative air assessments for tooth recovery. Record clinical assessment scores in the CRF or using source documentation for later transfer to the CRF.

Clinical examiner completes evaporative air sensitivity assessments (Schiff Sensitivity Scale only) on remaining eligible teeth identified at Screening. Record clinical assessment scores in the CRF or using source documentation for later transfer to the CRF.

The same examiner will be responsible for completing both clinical measures of DH (tactile and evaporative air sensitivity) for the duration of the study.

- Remind subject of dentifrice usage instructions; supervise dosing and brushing with study dentifrice and recording of brushing in the diary. Record in the CRF.
- Spontaneous reporting of adverse events and those elicited by asking subjects to respond to a non-leading question such as "How do you feel?" will be assessed. Any AEs/incidents reported on completion of the supervised brushing with the assigned study dentifrice will be recorded in the CRF.
- Remind the subject of the Lifestyle Guidelines ([Section 5.5](#)) and any Concomitant Medication/Treatment(s) requirements ([Section 6.8](#)) of the protocol. Record in the CRF.

8.2.3 Day 56 (± 2 days) (Visit 7)

Changes in health, concomitant medication or non-drug treatments/procedures will be documented in the CRF.

Spontaneous reporting of adverse events and those elicited by asking subjects to respond to a non-leading question such as “How do you feel?” will be assessed and any AEs recorded in the CRF.

The following procedures will then be completed at each visit.

- Complete visual checks of returned study dentifrice tubes and review completed diary. Record any suspected over or under use, and the number of any missed or additional brushings, in the CRF. *Do not return dentifrice/toothbrush/diary to subject.*
- Confirm subject adherence to the requirements of the protocol and continuance. Record in the CRF.
- Subject completes a DHEQ (source document), for later transcription into the CRF.
- Clinical examiner completes an OST examination. Record findings in the CRF.
- Clinical examiner completes an OHT examination. Record findings in the CRF.
- Clinical examiner completes sensitivity assessments for the two ‘test teeth’ selected at Baseline, first to a tactile stimulus and then to an evaporative air stimulus. The examiner will allow at least 5 minutes between the completion of the tactile assessments and the start the evaporative air assessments for tooth recovery. Record clinical assessment scores in the CRF or using source documentation for later transfer to the CRF.

Clinical examiner completes evaporative air sensitivity assessments (Schiff Sensitivity Scale only) on remaining eligible teeth identified at Screening. Record clinical assessment scores in the CRF or using source documentation for later transfer to the CRF.

The same examiner will be responsible for completing both clinical measures of DH (tactile and evaporative air sensitivity) for the duration of the study.

- Remind the subject to inform the site if they experience any untoward medical occurrence or use any medications in the next 5 days (that is, in the 5 days following their last dose of study treatment).
- Study conclusion.

8.3 Diary Review

The diary should be reviewed at every visit by the investigator, or suitably qualified designee, and the subject. Any subject comment captured in the diary which is considered an adverse event or incident will be assessed and reported as per the defined procedures in this protocol. Adverse event reporting procedures are summarized in Adverse Event and Serious Adverse Events ([Section 10](#)). Incident reporting procedures are summarized in Definition of and Procedure for Reporting Medical Device Incidents ([Section 10.9](#)).

Any additional comments relating to medications/treatments provided in the diary will be reviewed by the investigator or medically qualified designee with the subject and entered into the CRF as appropriate.

Additional and missed product applications will be considered deviations from the protocol and will be recorded on the Deviations Log.

8.4 Study Conclusion

The Study Conclusion page of the CRF will be completed for all subjects whether they completed all study procedures or if they were discontinued from the study early. If the subject discontinued early, at any point during the study, the primary reason for withdrawal should be recorded on the Study Conclusion page.

If a subject has any clinically significant, study-related abnormalities, AEs or incidents at the conclusion of the study, the GSK CH medical monitor (or designated representative) should be notified and, the subject may be asked to remain at the clinical site or be asked to return for a follow-up visit to ensure any issue is resolved or deemed not clinically significant.

8.5 Follow-up Visit/Phone Call

The study site may contact a subject to follow up an AE post-study completion/withdrawal and, in some circumstances, request they return to the site for additional follow-up visits (final safety assessments). If needed, additional oral examinations may be carried out at such visits.

9 STUDY ASSESSMENTS

Every effort should be made to ensure that protocol-required tests and procedures are completed as described. However, it is anticipated that from time to time there may be circumstances, outside the control of the investigator that may make it unfeasible to

complete an assessment. In these cases, the investigator must take all steps necessary to ensure the safety and well-being of the subject. When a protocol-required assessment cannot be performed, the investigator (or designee) will document the reason for the missed assessment as a protocol deviation and any corrective and preventative actions that he or she has taken to ensure that required processes are adhered to as soon as possible. The Sponsor must be informed of any missed assessments in a timely manner.

To ensure the clinical examiner/staff involved in efficacy and safety assessments remain blind to product received, throughout the study: site staff involved in the dispensing of study treatment and the supervision of on-site product usage will work in a separate area; the examiner will not be permitted in any area where study product is stored, dispensed, or in use; study subjects will be instructed not to remove study product from the opaque bags provided outside of the dispensing room, while at the study site; dispensing staff will not be involved in any safety/efficacy assessment procedure during the study.

9.1 Screening Assessments

Screening assessments to identify eligible teeth will be performed by appropriately trained clinical examiners at the times, and in the order, defined in the [Study Procedures](#) section of this protocol ([Section 8](#)). A single examiner will be responsible for the conduct of the clinical measures of DH (tactile and evaporative air sensitivity) for the duration of the study (at Screening and all subsequent visits).

Eligible tooth assessments will be accomplished by oral examination and will evaluate dentition exclusions, EAR, MGI, tooth mobility and sensitivity to tactile and evaporative air stimuli. Assessments will be carried out by the investigator, or qualified designee, against the inclusion/exclusion criteria. Ineligible subjects will not be re-screened.

9.1.1 Erosion, Abrasion and Recession (EAR)

The facial surfaces of all incisor, canine and pre-molar teeth that do not present any of the general dentition exclusion criteria, or specific dentition exclusion criteria for eligible teeth, will be examined for signs of cervical EAR ([Addy 2002](#)).

9.1.2 Modified Gingival Index (MGI)

The MGI is a non-invasive, visual assessment of gingival health ([Lobene et al. 1986](#)). MGI will be assessed for incisor, canine and pre-molar teeth exhibiting none of the dentition exclusions and facial/cervical EAR. MGI will be scored for the facial gingiva only, adjacent to the test area (exposed dentine). Eligible teeth will have a MGI score of zero.

| Score | Description |
|-------|--|
| 0 | Absence of inflammation |
| 1 | Mild inflammation; slight change in colour, little change in colour; little change in texture of any portion of the marginal or papillary gingival unit. |
| 2 | Mild inflammation; criteria as above but involving the entire marginal or papillary gingival unit. |
| 3 | Moderate inflammation; glazing, redness, edema, and/or hypertrophy of the marginal or papillary gingival unit. |
| 4 | Severe inflammation; marked redness, edema and/or hypertrophy of the marginal or papillary gingival unit, spontaneous bleeding, congestion, or ulceration. |

9.1.3 Tooth Mobility Assessment

Clinical mobility will be assessed for incisor, canine and pre-molar teeth exhibiting none of the dentition exclusions, facial/cervical EAR and a MGI = 0, using a modification of the Miller Index ([Laster et al. 1975](#)). Eligible teeth will have clinical mobility ≤ 1 .

| Degree | Description |
|--------|--|
| 0 | No movement or mobility of the crown of the tooth < 0.2 millimeter (mm) in a horizontal direction. |
| 1 | Mobility of the crown of the tooth $0.2 - 1$ mm in a horizontal direction |
| 2 | Mobility of the crown of the tooth exceeding 1 mm in a horizontal direction |
| 3 | Mobility of the crown of the tooth in a vertical direction as well. |

9.1.4 Qualifying Tactile Sensitivity

The tactile sensitivity of incisor, canine and pre-molar teeth exhibiting none of the dentition exclusions, and meeting the EAR, MGI and clinical mobility criteria, will be assessed using a constant pressure probe (Yeaple probe ([Polson et al. 1980](#))). The probe tip will be placed perpendicular to the facial surface of the tooth and drawn slowly across the exposed dentine to ensure application of the stimulus across the potentially ‘sensitive’ area. After each application, the subject will be asked to indicate whether they

experienced any pain or discomfort (yes/no response only). The subject may respond "yes" if they feel pressure as the probe is applied to their tooth. The examiner will remind them they should only respond 'yes' if they feel PAIN or DISCOMFORT. The gram setting which elicits the two consecutive 'yes' responses will be recorded as the tactile threshold (g). At Screening, the upper force setting will be 20 g. For a tooth to qualify at Screening, it must have a tactile threshold \leq 20 g. If no sensitivity is found at the upper setting, the tactile threshold will be recorded as $>$ 20 g and the tooth will be disqualified from further testing.

If a subject fails to give a definite answer, the examiner will re-prompt them to provide response. If uncertainty continues, this will be indicated on the clinical assessment score sheet/in the CRF. If the subject continues to be unsure, or the examiner is unsure of the reliability of their response, the examiner may opt to re-probe at the same force setting (indicated to the assistant by a non-verbal signal, i.e. a hand gesture), or move to the next force setting (10 g increase).

The examiner will generally make the pressure setting adjustments (may be carried out by an assistant/scribe); the scribe will record the micro-amperage setting and subject's responses.

Calibration of the Yeaple Probe:

The Yeaple probe will be calibrated by an appropriately trained member of the study staff (typically the clinical examiner or their assistant/scribe) before use on each day subjects are assessed. The microamp settings may vary from day to day (partly due to battery power consumption), but the difference should not be significant. Thus, previous probe settings can serve as a guide. Calibration should start at the lowest microamp setting and then increase. Either calibration method described below is acceptable.

- **Method 1 ('Water Cup'):** The Yeaple probe is fixed to a clamp attached to a ring stand so that the probe tip is vertical. A small paper cup attached with cotton thread is balanced over the end of the Yeaple probe, without the probe tripping. The probe dial is set to the microamp setting and water is fed into the paper cup using a dropper until the probe trips. The gram setting is recorded and the Yeaple probe reset to the next microamp value. The procedure is repeated until data has been collected to more than 80 g.
- **Method 2:** The Yeaple probe is fixed to a clamp attached to a ring stand so that the top is perpendicular to the pan of an ohaus dial-o-gram® balance or equivalent. The probe tip is positioned to just touch the pan when the balance is set at zero grams. The probe dial is set to the microamp setting and the gram

setting is increased on the balance until the probe trips. The gram setting is recorded and the Yeaple probe reset to the next microamp value.

The data are plotted, and the points connected with line segments in order to interpolate the micro-amp values equivalent to 10, 20, 30, 40, 50, 60, 70 and 80 g. This calibration should be repeated three times, and the average of the three used for the day's settings. The settings will be recorded on the Yeaple probe calibration record (along the probe's serial number) which will serve as the force setting guide for that day's examinations.

9.1.5 Qualifying Evaporative Air Sensitivity

Evaporative air sensitivity will be assessed on the facial surfaces of incisor, canine and pre-molar teeth exhibiting none of the dentition exclusions, and meeting the EAR, MGI, clinical mobility and tactile threshold (≤ 20 g) criteria, a minimum of 5 minutes after the tactile assessments have been completed. The assessment will be made by directing a one second application of air from a standard dental syringe held perpendicular to the tooth surface, approximately 1-2 mm coronal to the gingival margin, and from a distance of approximately 1 centimeter. The examiner will take appropriate measures to isolate the tooth surface to prevent stimulation of adjacent teeth or surrounding soft tissue.

Subject response to the stimulus will be evaluated using the Schiff sensitivity scale ([Schiff et al. 1994](#)). This is an examiner-based index, scored immediately following administration of the evaporative air stimulus. This scale focuses on a combination of specific, observable, physical, behavioural and verbal responses from the subject, which may facilitate discrimination. For a tooth to qualify at screening, it must have a Schiff sensitivity score ≥ 2 . If Schiff sensitivity score = 0 or 1, the tooth will be disqualified from further testing.

| Score | Description |
|--------------|--|
| 0 | Subject does not respond to air stimulation |
| 1 | Subject responds to air stimulus but does not request discontinuation of stimulus |
| 2 | Subject responds to air stimulus and requests discontinuation or moves from stimulus |
| 3 | Subject responds to stimulus, considers stimulus to be painful, and requests discontinuation of the stimulus |

9.2 Efficacy Assessments

The following efficacy assessments will be performed by an appropriately trained clinical examiner/staff (who are blind to product received), at the times and in the order defined in the Study Procedures section of this protocol ([Section 8](#)).

A single examiner will be responsible for the conduct of both clinical measures of DH (tactile and evaporative air sensitivity) for the duration of the study and the selection of the two ‘test teeth’ for all study subjects.

9.2.1 Dentine Hypersensitivity Experience Questionnaire (DHEQ-15)

A ‘short form’ DHEQ ([Appendix I](#) Example DHEQ) will be completed by each study subject at Baseline (Visit 2), Day 28 (Visit 3) and Day 56 (Visit 4), prior to the OST examination and the clinical efficacy assessments.

The DHEQ is divided into two sections - Section 1 asks questions about ‘*your sensitive teeth and the impact it has on your everyday life*'; Section 2 asks questions about ‘*the ways in which the sensations in your teeth affect you in your daily life*’ grouped into the following domains.

- Restrictions (Section 2, Q1-3)
- Adaptation (Section 2, Q4-6)
- Social Impact (Section 2, Q7-9)
- Emotional Impact (Section 2, Q10-12)
- Identity (Section 2, Q13-15)

At Baseline, all questions will be answered - Section 1 (Q1-9) and Section 2 (Q1-15); at Day 28 and Day 56, Section 1 (Q7-9 only) and Section 2 (Q1-15) will be answered.

9.2.2 Tactile Sensitivity

The tactile sensitivity of all teeth that exhibited none of the dentition exclusions, and met the EAR, MGI, clinical mobility and qualifying tactile threshold/Schiff sensitivity score criteria at Screening, will be assessed at Baseline (Visit 2). Teeth with a Baseline tactile threshold of ≤ 20 g will also be assessed for evaporative air sensitivity. The tactile sensitivity of the two ‘test teeth’ selected by the clinical examiner at Baseline will be assessed for randomised subjects at all subsequent visits (Visits 3-7).

The tactile stimulus will be administered, and subject response recorded, as described in [Section 9.1.4](#). The gram setting which elicits the two consecutive ‘yes’ responses will be recorded as the tactile threshold (g).

At Baseline (Visit 2), the upper force setting will be 20 g; at all subsequent visits (Visits 3-7), the upper force setting will be 80 g. If no sensitivity is found at the upper setting, the tactile threshold will be recorded as > 20 g at Baseline, and as > 80 g on Days 3, 7, 14, 28 and 56.

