1.4 Sample Size Calculation

No formal sample size has been produced for this exploratory clinical study to characterize the DH efficacy profile of the Investigational Product (IP), as measured by Schiff sensitivity score and tactile threshold, over time. Based on previous GSK CH studies evaluating DH efficacy of 0.454% w/w SnF_2 dentifrices, approximately 50 evaluable subjects per treatment group is considered sufficient to provide reliable estimates of treatment effect for the purposes of this study and to aid in the design of future clinical studies. Approximately 104 subjects will be randomized to study treatment (approximately 52 per treatment group) to achieve approximately 50 evaluable subjects per treatment group, allowing for a dropout rate of approximately 4%.

2 Planned Analyses

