3.1 Baseline Definition

For all endpoints, the baseline value will be the Day 0 (Visit 2) pre-treatment assessment with a non-missing value.

Unless otherwise stated, if baseline data is missing no derivation will be performed and will be set to missing.

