4.4.1 Primary Efficacy Endpoints

4.4.1.1 Primary Efficacy Endpoint Definition

The primary efficacy variables are Schiff sensitivity score and tactile threshold (g), both calculated as the average score of the two test teeth, and the number of sensitive teeth

(Schiff sensitivity score ≥ 1) at Day 0 (Baseline), Day 3, Day 7, Day 14, Day 28 and Day 56.

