4.4.3 Handling of Missing Values/Dropouts/Discontinuations

Subjects who withdraw from the study early will be included in the study analysis up to the point of withdrawal. Subjects who withdraw will not be replaced. No data will be imputed in the case of dropouts or missing data.

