4.5.1.2.1 Secondary Efficacy Endpoint 2 Definition

The second Secondary Efficacy Variable is change from Baseline in tactile threshold (g) at Day 56. Change from Baseline will be derived for the individual teeth first before calculating the average change for the two test teeth.

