4.5.1.2.2 Statistical Hypothesis, Model and Method of Analysis

Study product differences will be tested under the null hypothesis:

- H_0 : there is no treatment difference versus the alternate hypothesis;
- H_1 : there is a treatment difference

Change in tactile threshold (g) will be analysed at Day 56 using an ANCOVA model with study product and Baseline Schiff stratification included as factors and Baseline tactile threshold included as a covariate.

Using the above model, adjusted mean change from Baseline, along with 95% CIs will be reported by study product group. P-values testing for non-zero change from Baseline will be presented for both study product groups. Mean difference between study product groups, 95% CIs and p-values will be provided for tactile threshold (g) in [Table 14.2.2.5.1](#). Significance testing will be conducted at the two-sided 5% significance level; no adjustment for multiple comparisons will be made.

The assumption of normality and homogeneity of variance in the ANCOVA model will be investigated, and if violated, an appropriate data transformation or non-parametric method, for example, the van Elteren test, adjusting for the maximum baseline Schiff Sensitivity scores, will be performed.

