4.7.1.2 Statistical Hypothesis, Model and Method of Analysis

Study product differences will be tested under the null hypothesis:

- H_0 : there is no treatment difference versus the alternate hypothesis;
- H_1 : there is a treatment difference

Change from Baseline in Schiff sensitivity score and tactile threshold (g) at Days 3, 7, 14 and 28 will be analyzed as per the secondary analyses: adjusted mean change from Baseline, along with 95% CIs will be reported by study product group ([Table 14.2.2.4.1](#) and [Table 14.2.2.5.1](#) respectively). Study product differences and 95% CIs will also be presented. No p-values will be reported.

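### Does it matter that the plan gives no gram value for a tactile reading above 80 g?

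*Protocol*

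**What the plan says.** At Visits 3 to 7 the upper probe force is 80 g (Protocol 9.2.2). If the tooth does not respond there, "the tactile threshold will be recorded as > 20 g at Baseline, and as > 80 g on Days 3", 7, 14, 28 and 56. The post-Baseline entry is therefore an inequality.

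The analysis treats tactile threshold as a number:

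- SAP 4.4.1.1 defines the Schiff and tactile variables as "both calculated as the average score of the two test teeth".
- SAP 4.5.1.2.1: "Change from Baseline will be derived for the individual teeth first before calculating the average change for the two test teeth".
- SAP 4.5.1.2.2: "Change in tactile threshold (g) will be analysed at Day 56 using an ANCOVA model".
- SAP 4.7.1.2 carries this to the earlier visits: change in "tactile threshold (g) at Days 3, 7, 14 and 28 will be analyzed as per the secondary analyses".

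Two nearby rules deal with other situations. SAP 3.1 says that "if baseline data is missing no derivation will be performed and will be set to missing", which concerns Baseline only. SAP 4.4.3 says "No data will be imputed in the case of dropouts or missing data", which concerns absent data.

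The sample of about 50 evaluable subjects per group is "considered sufficient to provide reliable estimates of treatment effect for the purposes of this study" (SAP 1.4). There is no formal sample size calculation.

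**The concern.** A tooth that does not respond at 80 g shows the largest benefit the probe can register. If the numerical value of that result is not fixed, the tactile estimate in grams is not fully defined before unblinding. This touches the descriptive tactile summaries, the Day 56 tactile comparison (one of two tested secondary endpoints) and the Day 3 to 28 estimates. Because the sample size is justified by the quality of the estimates and their use in designing later studies, the estimate itself is a product of the trial.

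The worst case would be a non-numeric entry that is silently read as missing. The most improved teeth would then drop out, more of them from the better arm, and the difference would shrink. A coding chosen after the results were seen could also raise the false-positive rate.

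The fallback in SAP 4.5.1.2.2 (a transformation or the van Elteren test) does not avoid the question, because the two teeth are averaged before anything is transformed or ranked.

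**Working it through.** **Inputs from the documents.** Upper force 80 g after Baseline (Protocol 9.2.2); settings in 10 g steps from 10 to 80 g (Protocol 9.1.4); both test teeth at 20 g or less at Baseline (Protocol 5.2 and 9.2.4); about 50 evaluable per group (SAP 1.4). The plan's own figure is consistent: 52 x 0.96 = 49.9. Because of the Baseline criterion, a > 20 g entry can never belong to a test tooth, so only > 80 g after Baseline is in question.

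**Not in the documents.** The share of readings above 80 g, the tactile SD and the expected effect. All simulated figures below rest on assumptions.

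**Step 1: exact shift.** If a reading above 80 g is coded v, the unadjusted difference, compared with coding it 80, moves by

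(v - 80) x (share of Test teeth above 80 g - share of Control teeth above 80 g).

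For a gap of 5, 10 or 20 percentage points, v = 90 gives 0.5, 1.0 or 2.0 g.

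**Step 2: the planned ANCOVA.** Assumed: 50 per arm, lognormal thresholds read on the 10 g grid, log-SD 0.7, tooth correlation 0.5, Baseline 10 or 20 g (60/40), true shift 0.5 SD, 4000 simulated trials per row.

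| Above 80 g, Control / Test | Difference coded 80 (power) | Difference coded 90 (power) | Move |
|---|---|---|---|
| 1% / 3% | 7.61 g (76%) | 7.84 g (75%) | 0.23 g |
| 2% / 6% | 8.60 g (77%) | 9.00 g (77%) | 0.40 g |
| 5% / 13% | 9.71 g (77%) | 10.47 g (77%) | 0.76 g |
| 10% / 22% | 10.27 g (78%) | 11.43 g (78%) | 1.16 g |
| 20% / 37% | 9.96 g (78%) | 11.64 g (80%) | 1.68 g |

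The last column agrees with step 1: in the 10% row, 10 x (0.22 - 0.10) = 1.2 g. In relative terms the move runs from 0.23/7.61 = 3% to 1.68/9.96 = 17%. The half-width of the 95% interval, coded 80, is 5.6 to 7.3 g over these settings, so the move is roughly 4% to 23% of it. With a 0.2 SD shift at 10% ceiling the move is 4.51 - 4.10 = 0.41 g.

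**Step 3: the test.** The two codings give different 5% verdicts in 2-3% of trials. With no true effect each rejects in 4.5% to 5.5% of trials. Taking whichever of the two looks better rejects in 4.8% to 5.5% at ceilings of 2% to 20%.

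**Step 4: planning a later trial.** A higher code raises the difference and the SD together. A second set of assumptions (log-SD 0.8, medians 50 and 35 g, 28% and 15% of readings above 80 g, no covariates) shows this. For 90% power at two-sided 5%, n per arm = 2 x (1.960 + 1.282)^2 x (SD/difference)^2 = 21.01 x (SD/difference)^2.

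| Code | Difference | SD | Difference/SD | n per arm |
|---|---|---|---|---|
| 80 | 9.68 | 20.1 | 0.482 | 91 |
| 81 | 9.80 | 20.3 | 0.483 | 91 |
| 90 | 10.96 | 22.6 | 0.485 | 90 |
| 100 | 12.24 | 25.4 | 0.482 | 91 |

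Under the ANCOVA assumptions of step 2, the sizes coded 80 and 90 are 70 and 72, 68 and 68, and 71 and 70 per arm at Control ceilings of 2%, 10% and 20%.

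**The case for a change.** The strongest case for a change is that the estimate in grams is what the trial is meant to deliver, and it moves by up to 17% between two reasonable codes. One sentence would settle it. If readings above 80 g were set to missing, the loss would be real: at a 20% Control ceiling the difference falls to 6.5 g and power to 44%. If the analyst could pick after unblinding among coding 80, coding 90, dropping the tooth and dropping the subject, the error rate would reach 7.9% to 10.5%.

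Part of this stands. The mean in grams does depend on a convention, and anyone comparing it with another study should know which one was used. The plan would read better with the value stated.

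The large figures do not carry over. They require observed readings to be discarded, and nothing in either document says so. Protocol 9.2.2 makes > 80 g a recorded result, while SAP 4.4.3 speaks of dropouts and missing data. Protocol 12.2.2 has any exclusion of data decided at a blinded review meeting before database lock, so discarding such readings after the codes are released is already barred. What remains open is the choice among numerical codes, and steps 2 to 4 show how little turns on it. Nor is 90 g clearly the better value: the probe is calibrated to settings up to 80 g, and 90 g is a convention.

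**Conclusion.** The silence is real, but it is a gap that an analyst fills sensibly: an observed reading above the scale is entered at the top of the scale or one step beyond. No stated rule produces a wrong result, so no change to the plan is called for.

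Under the assumed ceiling rates of 1% to 20% in Control and a 0.5 SD effect, coding 90 g rather than 80 g moves the tactile difference by 0.2 to 1.7 g. Power changes by no more than about 2 points, type I error stays close to 5%, and a later trial's size changes by at most 2 per arm. If the true ceiling rate were well above 20%, the move in grams could be larger. It would still be 10 g times the between-arm gap in the share of such teeth. SAP 4.4.1.2 lists the tactile values of the test teeth by subject and visit, so that share can be counted from the listing.

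The reach is also limited. The study is exploratory, its primary analysis is descriptive, the Day 3 to 28 comparisons carry no p-values, and the between-group success statement in Protocol 3 names only the Schiff score.

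The content of SAP Attachment 1 and the Blind Data Review Plan was not available, so a stated value may exist there.
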